5. Willingness to utilize two reliable forms of contraception (for both males and females of childbearing potential) from Screening to one month after the last dose of study drug

Key Exclusion Criteria:

1. Known active infection with hepatitis B virus (HBV) and/or human immunodeficiency virus (HIV)
2. History of renal transplant and/or severe renal impairment defined as eGFR (estimated glomerular filtration rate) of less than 30 mL/min/1.73 m²
3. Evidence of tumor burden >Milan criteria, or evidence of micro- or macrovascular invasion in explanted liver
4. Hepatocellular carcinoma (HCC) at entry into the study
5. Concurrent sirolimus (rapamycin) use

Title: A Multicenter, Double-Blind, Randomized Trial of IDN-6556 in Subjects Who had Hepatitis C Virus (HCV) Reinfection and Liver Fibrosis or Cirrhosis following Orthotopic Liver Transplantation for Chronic HCV Infection and Who Subsequently Achieved a Sustained Virologic Response Following anti-HCV Therapy

6. History or presence of clinically concerning cardiac arrhythmias, or prolongation of Screening (pre-treatment) QTcF interval of > 480 milliseconds (msec)
7. Subjects with diagnosed or suspected systemic lupus erythematosus (SLE) and/or rheumatoid arthritis (RA)
8. If female: known pregnancy, positive urine or serum pregnancy test, or lactating/breastfeeding.

Criteria for Evaluation:**Safety Variables:**

Safety evaluations will be based on adverse event (AE) reports. These will be coded using MedDRA to preferred terms, sorted by body system, and compared between the two treatment groups.

1. Serious adverse events will be analyzed separately
2. Clinical laboratory variables will be evaluated in the context of coinciding clinical adverse events when necessary

Efficacy Variables:Efficacy Endpoints:

- Ishak Fibrosis Score
- Necro-inflammatory sub-score of the modified Histological Activity Index
- Biomarkers of apoptosis
- Liver function (e.g., ALT, AST, bilirubin)
- Transient elastography (to be performed at select centers only)

Exploratory Endpoint:

- Morphometric image analysis to quantify collagen deposition

Statistical Methods:

All endpoints will be tested at a two-sided statistical significance level of 0.05.

For the comparison of Ishak Fibrosis Scores at 24 months, subjects will be classified into one of the following three categories:

- Category 1. Regression at 24 months defined as a greater than or equal to a one point improvement in Ishak Fibrosis Score from Baseline.

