4.2 Study Rationale

The Investigator's Brochure (IB) contains a summary of the data and information collected about IDN-6556 (including principal data and findings from preclinical, toxicological, and clinical studies conducted to date).

IDN-6556 is a novel small molecule irreversible caspase inhibitor. Caspases are enzymes responsible for executing apoptotic pathways, or programmed cell death, and activating cytokines such as IL-1 β and IL-18. The apoptotic pathway has been previously shown to play an important role in the formation and progression of hepatic fibrosis, leading to the hypothesis that inhibition of caspases may have significant therapeutic benefit for the treatment of liver fibrosis, independent of the underlying disease state (e.g., viral infection, fatty liver, etc.). Activation of pro-inflammatory cytokines such as IL-1 β has also been shown to play a role in hepatic injury. IDN-6556 has shown specificity in assays measuring caspase inhibition, and prevented apoptosis in a variety of cellular assays. IDN-6556 demonstrated efficacy in a number of animal models of liver disease, as well as in models of damage to other organ systems. Human studies have demonstrated that IDN-6556 can lower serum transaminases after intravenous or oral administration. Treatment with IDN-6556 was also associated with statistically significant reductions in elevated activated serum caspases and cCK18, a caspase cleaved substrate, indicating that IDN-6556 works by the presumed mechanism of action of inhibiting caspases.

In subjects who received a liver transplant and were successfully treated and achieved an SVR, fibrosis and inflammation were still present up to 5 years after treatment^{9,10,11}. In general, fibrosis stabilized or regressed in most subjects with increases in fibrosis in only a small subset of subjects. In general, inflammation/necro-inflammation was still present, but reduced as compared to pre-treatment. A caspase inhibitor, such as IDN-6556, could have clinical utility by reducing apoptosis rates and inflammation, which would also reduce the stimulus for fibrogenesis. Given this rationale, this study will evaluate the efficacy and safety of IDN-6556 in subjects with chronic hepatitis C virus (HCV) infection who have undergone

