7.1 Inclusion Criteria

To participate in this study, subjects must meet **all** of the following criteria:

1. Male or female subjects of minimum adult legal age (according to local laws for signing the informed consent document), able to provide written informed consent, and able to understand and willing to comply with the requirements of the study
2. History of orthotopic liver transplantation for HCV-induced liver disease
Note: Living donor or cadaveric transplantation will be permitted into the study. HCV positive donor livers will also be permitted into the study.
3. Diagnosis of HCV infection (HCV-RNA detectable in serum) and liver fibrosis or cirrhosis status post liver transplantation, and achieved a sustained virologic response (SVR) with anti-viral HCV treatment within 18 months of Day 1
Note: For the purposes of this study, subjects must meet the definition of SVR as defined by the anti-HCV regimen used.
4. Liver fibrosis or cirrhosis on liver histology as read by central histopathologist of Ishak F2 to F6 within three months of Day 1
Note: Baseline liver histology in close approximation of the three month window may be permitted on a case by case basis after discussion with the Medical Monitor.
5. Available liver tissue for central read (ten, 4-microns-thick, unstained liver sections)
6. Willing to undergo protocol-determined liver biopsies during the study
7. Hemoglobin ≥ 11 g/dL, platelet count $\geq 75 \times 10^9/L$, WBC $\geq 2.0 \times 10^9/L$
Note: As these parameters may be influenced by immunosuppressive therapy, small variances may be permitted on a case by case basis after discussion with the Medical Monitor.
8. On stable doses of immunosuppressant therapy for ≥ 3 months prior to Day 1
9. Willingness to utilize two reliable forms of contraception (for both males and females of childbearing potential) from Screening to one month after the last dose of study drug

Title: A Multicenter, Double-Blind, Randomized Trial of IDN-6556 in Subjects Who had Hepatitis C Virus (HCV) Reinfection and Liver Fibrosis or Cirrhosis following Orthotopic Liver Transplantation for Chronic HCV Infection and Who Subsequently Achieved a Sustained Virologic Response Following anti-HCV Therapy

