8.2.2 Secondary

The secondary efficacy endpoint will be the effects on liver inflammation measured by the difference in responder rates in the necro-inflammatory sub-score of the modified Histological Activity Index between the two treatment groups (change defined as a movement by at least 2 points at 24 months compared with Baseline).

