12.2.2 Efficacy Variables

The following parameters will be recorded for the efficacy evaluation:

- Histologic changes defined as ≥ 1 point change in the Ishak Fibrosis Score
- Effects on liver inflammation in the necro-inflammatory sub-score of the modified Histological Activity Index. A responder will be defined as a subject who has improved by at least 2 points at 24 months on the necro-inflammatory sub-score of the modified Histological Activity Index from Baseline.
- Clinical outcomes defined as time to clinical worsening. Time to decompensation, re-transplantation, and/or death will be captured as clinical outcomes. (Note: Decompensation is defined as presence of: bleeding varices, encephalopathy, ascites requiring treatment and jaundice.)
- Effects on biomarkers of apoptosis and mechanism of action
- Effects on liver function parameters such as ALT, AST, bilirubin
- Changes in transient elastography (at select centers)

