12.5 Sample Size

The sample size determination for this study is based on the Phase 2b screening methodology presented in Fleming and Richardson¹².

A total of 60 subjects will be treated in a 2:1 ratio to IDN-6556 or placebo. Treatment duration for all subjects will be two years. The primary outcome variable is change in Ishak Fibrosis Score at 24 months.

The primary analysis of this Phase 2 “screening” study is formally based on a three-category decision guideline. To be specific, the decision guideline for this study is based on whether the proportion of subjects who show a regression (i.e., improvement) of Ishak Fibrosis Score at 24 months for the IDN-6556 arm compared to the placebo arm is less than 5%, is from 5% up to 15%, or is at least 15%.

Note that these categories should not be interpreted as providing strict decision rules but rather as guidelines that will be factored into a broader scientific assessment of the benefit to risk profile of the IDN-6556 regimen. This broader assessment will include consideration of safety, of secondary efficacy endpoints, and of relevant information external to this study. Specifically, the decision guidelines for this study are:

1. If the estimated absolute increase in the proportion of subjects who show regression in Ishak Fibrosis Score is less than 5%, (e.g., less than an estimated increase from 30% to 35%), then the IDN-6556 regimen is not plausibly more efficacious than placebo; the formulation of this IDN-6556 regimen or its utility in this indication will be reconsidered.
2. If the estimated absolute increase in the proportion of subjects who show regression in Ishak Fibrosis Score is from 5% up to 15%, (e.g., an estimated increase from 30% to between 35% and 45%), then the IDN-6556 regimen is

Title: A Multicenter, Double-Blind, Randomized Trial of IDN-6556 in Subjects Who had Hepatitis C Virus (HCV) Reinfection and Liver Fibrosis or Cirrhosis following Orthotopic Liver Transplantation for Chronic HCV Infection and Who Subsequently Achieved a Sustained Virologic Response Following anti-HCV Therapy

plausibly more efficacious than placebo and if analyses of biomarkers suggest utility of the IDN-6556 regimen, should be evaluated definitively in a subsequent Phase 3 clinical study.

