APPENDIX II: LIVER BIOPSY SCORING AND ASSESSMENT

Ishak Modified Histological Activity Index (Ishak Fibrosis Score)

Liver biopsy findings are assigned scores for fibrosis as follows:

Table II.1 Ishak Fibrosis Score: Architectural Changes, Fibrosis and Cirrhosis

| | Score |
|--|-------|
| No fibrosis | 0 |
| Fibrous expansion of some portal areas, with or without short fibrous septa | 1 |
| Fibrous expansion of most portal areas, with or without short fibrous septa | 2 |
| Fibrous expansion of most portal areas, with occasional portal to portal bridging | 3 |
| Fibrous expansion of portal areas, with marked bridging (portal to portal as well as portal to central) | 4 |
| Marked bridging (portal to portal and/or portal to central) with occasional nodules (incomplete cirrhosis) | 5 |
| Cirrhosis probable or definite | 6 |

Ishak Modification of Knodell Histological Activity Index

Liver biopsy findings will be assigned scores for necro-inflammation as follows:

Table II.2 Ishak Modification of Knodell Histological Activity Index: Necro-inflammatory Scores

| | Score |
|--|-------|
| A Periportal or periseptal interface hepatitis (piecemeal necrosis) | |
| Absent | 0 |
| Mild (focal, few areas) | 1 |
| Mild/moderate (focal, most portal areas) | 2 |
| Moderate (continuous around <50% of tracts or septa) | 3 |
| Severe (continuous around >50% of tracts or septa) | 4 |
| B Confluent necrosis | |
| Absent | 0 |
| Focal confluent necrosis | 1 |
| Zone 3 necrosis in some areas | 2 |
| Zone 3 necrosis in most areas | 3 |
| Zone 3 necrosis + occasional portal-central bridging | 4 |
| Zone 3 necrosis + multiple portal-central bridging | 5 |

Title: A Multicenter, Double-Blind, Randomized Trial of IDN-6556 in Subjects Who had Hepatitis C Virus (HCV) Reinfection and Liver Fibrosis or Cirrhosis following Orthotopic Liver Transplantation for Chronic HCV Infection and Who Subsequently Achieved a Sustained Virologic Response Following anti-HCV Therapy

| | |
|---|---|
| Pan acinar or multiacinar necrosis | 6 |
| C Focal (spotty) lytic necrosis, apoptosis and focal inflammation | |
| Absent | 0 |
| One focus or less per 10X objective | 1 |
| Two – Four foci per 10X objective | 2 |
| Five – Ten foci per 10X objective | 3 |
| More than ten foci per 10X objective | 4 |
| D Portal Inflammation | |
| None | 0 |
| Mild, some or all portal areas | 1 |
| Moderate, some or all portal areas | 2 |
| Moderate/marked, all portal areas | 3 |
| Marked, all portal areas | 4 |

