4 PLANNED SIZE DETERMINATION

This study will be conducted at multiple centers at which approximately 60 subjects will be enrolled and treated in a 2:1 ratio with emricasan or placebo, respectively. The sample size determination for this study is based on the Phase 2b screening methodology presented in [Fleming and Richardson \(2004\)](#).

The base case for the placebo response rate of 30% was assumed and obtained from [George, et al \(2009\)](#), where it stated that 29% of patients showed a response in fibrosis from a mean of 1.6 years following HCV-SVR.

Treatment duration for all subjects is expected to be two years. The primary analysis of this Phase 2 “screening” study is formally based on a three-category decision guideline. The decision guideline for this study is based on whether the difference in the proportions of subjects who show a response (i.e., improvement or no change) per their Ishak Fibrosis Score at 24 months for emricasan compared to placebo is less than 5%, is from 5% up to 15%, or is more than 15%. Specifically, the outcome of the study will determine one of the following three course of action:

1. If the difference in response rates between emricasan and placebo (i.e., emricasan response rate – placebo response rate) is less than 5%, then emricasan regimen is not plausibly more efficacious than placebo; hence, emricasan or its utility in this indication will be reconsidered.
2. If the difference in response rates between emricasan and placebo is from 5% up to 15%, then emricasan is plausibly more efficacious than placebo in this indication if secondary analyses of biomarkers suggest utility of emricasan or a positive safety profile is observed; hence, emricasan could be evaluated in a subsequent Phase 3 clinical study.
3. If the difference in response rates between emricasan and placebo is more than 15%, then emricasan could be evaluated in a subsequent Phase 3 study.

These categories should not be interpreted as providing strict decision rules but rather as guidelines that will be factored into a broader scientific assessment of the benefit to risk profile for emricasan in this indication. This broader assessment will include consideration of secondary efficacy analyses, safety profile, and relevant information external to this study.

The operating characteristics for this three-category decision guideline are shown in Table 1.

Table 1. Operating Characteristics for Three-Category Decision Guideline

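### The 2-point necro-inflammatory responder rule excludes subjects who start at 0 or 1 from ever responding, and the SAP drops the rule without supplying the treatment-effect estimate that the protocol promises

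*Protocol*

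**What the plan says.** Protocol 8.2.2 names one secondary efficacy endpoint, the between-arm difference in responder rates on the necro-inflammatory sub-score, with "change defined as a movement by at least 2 points at 24 months compared with Baseline". That wording has no direction. Section 12.2.2 supplies it: "A responder will be defined as a subject who has improved by at least 2 points at 24 months".

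Appendix II scores four items ("Liver biopsy findings will be assigned scores for necro-inflammation as follows"), each starting at 0. The maxima are 4, 6, 4 and 4.

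The histological entry requirement in 7.1 concerns fibrosis only: "Liver fibrosis or cirrhosis on liver histology as read by central histopathologist of Ishak F2 to F6 within three months of Day 1". Neither 7.1 nor 7.2 sets a lower limit on necro-inflammatory activity. On what to expect in this population, 4.2 says: "In general, inflammation/necro-inflammation was still present, but reduced as compared to pre-treatment".

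On analysis, the synopsis states "All endpoints will be tested at a two-sided statistical significance level of 0.05". Protocol 12.6.3 promises a treatment-effect estimate with a 95% confidence interval for the activity score, from an ordinal model to be detailed in the SAP. Protocol 12.1 allows the SAP to modify the protocol's plans.

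The SAP contains no 2-point responder. Section 9.2.3 summarises each of the four items separately, by category and by shift from baseline. It has no total score, between-arm estimate or interval. The Cochran-Mantel-Haenszel tests in 9.2.1 apply to the fibrosis response of 9.1. SAP section 14, which lists changes in the planned analysis, does not mention the loss of the responder endpoint or of the ordinal model.

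**The concern.** A scale with a floor at 0 and a rule that needs a 2-point fall make some subjects certain non-responders. Anyone with a baseline sub-score of 0 or 1 stays in the denominator of their arm and cannot enter the numerator, whatever the drug does. All subjects have already cleared the virus, so low baseline scores are plausible.

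At stake is the stated secondary objective on necro-inflammation, which is close to the drug's proposed mechanism. The protocol's endpoint would report a diluted effect. The SAP's replacement describes categories item by item, so a reader gets no single measure of the treatment effect on inflammation and no statement of its precision.

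**Working it through.** **Inputs.** From the documents: 40 v 20 subjects ("A total of 60 subjects will be treated in a 2:1 ratio to IDN-6556 or placebo"), two-sided 0.05, and a floor of 0 on each item. I take the sub-score as the sum of the four items, so its range is 0 to 4 + 6 + 4 + 4 = 18. Not in the documents, so assumed and varied: the share f of subjects starting at 0 or 1, and the response rates among those able to respond.

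**The plan's own figures.** Protocol 12.5 gives power for fibrosis regression of 20% at a true increase of 15 points and 80% at 37 points. SAP section 4 supplies the placebo rate: "The base case for the placebo response rate of 30% was assumed". Exact enumeration of the uncorrected two-proportion test with 40 v 20 gives 20% for 30% v 45% and 80% for 30% v 67%, so the plan's figures reproduce. No power is stated for the necro-inflammatory endpoint.

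**Dilution.** Let p1 and p0 be the response rates among subjects with baseline ≥2. Subjects below 2 respond with probability 0 in both arms, and randomisation makes f equal across arms in expectation. The rates over all subjects are therefore (1 − f)p1 and (1 − f)p0, and the difference is (1 − f)(p1 − p0).

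**Illustration with p1 = 50% and p0 = 20%** (pooled z-test; in the last column the number with baseline ≥2 varies binomially):

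| f | Rates, all subjects | Difference | Power, all 60 | Power, baseline ≥2 only |
|---|---|---|---|---|
| 0 | 50% v 20% | 30 points | 65% | 65% |
| 10% | 45% v 18% | 27 points | 57% | 59% |
| 25% | 37.5% v 15% | 22.5 points | 46% | 51% |
| 40% | 30% v 12% | 18 points | 33% | 42% |

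Restricting the analysis recovers 2, 5 or 9 percentage points of power, because the restricted comparison has fewer subjects.

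**Other assumed rates** (pooled normal approximation). With 30% v 67%, borrowed from the fibrosis calculation, power on all 60 falls from 79% at f = 0 to 60% at f = 20% and 31% at f = 50%. With 30% v 45% it falls from 19% to 14% and 9%. The direction is the same throughout, and the size depends on the assumptions.

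**Using the whole score.** Assumed model: Poisson baseline score with mean 3 or 2. Each baseline point is retained at Month 24 with probability 0.40 on drug and 0.75 on placebo, plus a new Poisson(0.4) component. The share at 0–1 is e⁻³(1 + 3) = 20% or e⁻²(1 + 2) = 41%. Simulated power, accurate to one or two points:

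| Share at 0–1 | 2-point rule, all | 2-point rule, baseline ≥2 | Total score adjusted for baseline |
|---|---|---|---|
| 20% | 73% | 78% | 94% |
| 41% | 46% | 54% | 76% |

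Type I error of the adjusted analysis is about 5%. Of the 21-point gain in the first row (94 − 73), 5 points come from removing floor subjects and 16 remain. Of the 30-point gain in the second (76 − 46), 8 come from removing them and 22 remain. Roughly three quarters of the gain is therefore due to not dichotomising. The model did not include the stratum covariate.

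**The case against.** The strongest reply is that the operative plan has no responder test. The SAP may modify the protocol, and it reports the activity index descriptively. A reader might infer that the trial as planned loses power on this endpoint. The documents do not support that, because the SAP runs no responder test that could lose it. This stands, and it limits the dilution argument to the protocol's endpoint as defined or to any later report of it. It does not answer the second half of the point: the estimate and interval promised in 12.6.3 are missing from the SAP, and section 14 does not say so.

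Second, f is unknown. Section 4.2 makes low scores plausible but does not show that anyone will total 0 or 1 out of 18. This stands too, and no definite loss can be claimed.

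Third, 12.6.3 names an ordinal model, which need not use the 2-point cut, and shift tables display baseline categories. This is partial mitigation. The protocol does not say the model adjusts for baseline activity, and the SAP does not carry the model forward.

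Fourth, this is a secondary endpoint in a Phase 2 screening study sized on fibrosis. The go/no-go guideline rests on fibrosis, with secondary endpoints only part of a broader assessment. That is correct and lowers the priority.

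Two further inferences should be resisted. Certain non-responders do not bias the randomised comparison or inflate type I error; they dilute it. And the gap between the 2-point rule and the adjusted total score is not a measure of the floor, since most of it comes from dichotomising.

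**Conclusion.** The floor is real. It follows from the 2-point improvement rule, a scale that starts at 0 and the absence of any minimum activity score at entry. The responder difference is multiplied by (1 − f), and nothing in the entry criteria makes f zero. The amount lost cannot be fixed from the documents: it is nil at f = 0, and under the assumed 50% v 20% rates it is 3, 7.5 or 12 points of difference at f = 10%, 25% or 40%.

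The SAP avoids the floor only by dropping the endpoint. It does so without naming the change, and it leaves the secondary objective on necro-inflammation without a total score, estimate or interval. A baseline-adjusted analysis of the total sub-score would remedy both weaknesses. Its power advantage (about 94% v 73%, or 76% v 46%) rests on an assumed score model. Priority: consider.

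**What to change.** In SAP 9.2.3, with matching wording in protocol 8.2.2 and 12.2.2:

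1. Define the necro-inflammatory sub-score as the sum of the four items, 0–18. Compare the Month 24 total between arms, adjusted for baseline sub-score and randomisation stratum (F2, F3–F5, F6), and report the estimate with its 95% CI. An ordinal model with the same covariates is equally acceptable and stays closer to 12.6.3.
2. If the 2-point responder rate is also reported, show it among subjects with baseline ≥2 alongside all subjects, and give the number per arm who could not respond. Baseline is measured before treatment assignment, so the restricted comparison remains a fair randomised one.
3. Record in SAP section 14 what happened to the protocol's responder endpoint and ordinal model.

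The cost is one extra model on scores already collected and a smaller denominator in the restricted table. No additional biopsy or change in conduct is needed. SAP 8.4 already tabulates the four items at baseline, so the share starting at 0 or 1 can be counted from blinded data before database lock.
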